1.1 Non-clinical Pharmacology

1.2 Non-clinical Safety Pharmacology

1.3 Non-clinical Pharmacokinetics

[REDACTED]

[REDACTED]

[figure not shown]
[REDACTED]

[REDACTED]

[REDACTED]

1.4 Non-clinical Toxicology

[REDACTED]

1.5 Clinical Studies

A first in human Phase I study (MT-7117-E01), evaluating the safety, tolerability, pharmacokinetics and pharmacodynamics of single and multiple ascending doses of

MT-7117 in healthy subjects, has completed dosing and data are available. The study was divided into eight parts; Part A: single ascending doses, Part B: suspension food effect, Part C: tablet food effect, Part D: gender effect, Part E: multiple ascending doses, Part F: ethnicity effect (Black/Afro-Caribbean subjects), Part G: ethnicity effect (Japanese subjects) and Part H: age effect. A total of 96 healthy volunteers received single oral doses of MT-7117 or placebo in 12 cohorts (dose range [redacted] to [redacted] and 48 healthy volunteers received multiple oral doses (dose range [redacted] to [redacted] for 14 days) of MT-7117 or placebo in 4 cohorts. All volunteers were male except for Part D in which a cohort of 8 female subjects were administered a single dose of [redacted] MT-7117 or placebo.

Single oral doses of MT-7117 did not cause any safety concerns in healthy Caucasian male subjects at dose levels of [redacted] to [redacted] in the fasted state, and at a dose level of [redacted] in the fed state. In addition, single doses of [redacted] MT-7117 were well tolerated in healthy Caucasian female, Black/Afro-Caribbean, Japanese and elderly Caucasian male subjects. Following multiple oral doses of MT-7117 up to [redacted] for 14 days, the most frequently reported treatment-emergent adverse events (TEAEs) were skin-related; including formation of new freckles, formation of new lentigines, formation of new nevi, darkening and increase in size of pre-existing nevi, increased skin tan, darkening of facial hair and increased color of tattoos. Lips and glans penis skin were involved in these reports in addition to the body skin. There were signs of reversibility of these skin events during the follow-up period. These skin events were considered to be related to the pharmacological effects of the study medication.

Dose-proportional increases in systemic exposure based on AUC and C_{max} were observed over the single dose range of [redacted] to [redacted]. Following multiple doses at [redacted], [redacted], [redacted], and [redacted] MT-7117 was rapidly absorbed with median t_{max} values ranging from 4 to 5 hours post-dose on both Day 1 and Day 14. Mean $t_{1/2}$ values ranged from 6.28 to 15.55 hours on Day 1 and 10.56 to 18.97 hours on Day 14. Systemic exposure to MT-7117 in plasma, based on calculation of AUC and C_{max} , appeared to increase in a slightly more than dose-proportional manner over the [redacted] to [redacted] dose range. Steady-state was generally reached by 5 days of multiple dosing.

2. STUDY OBJECTIVES AND ENDPOINTS

2.1 Study Objectives

2.1.1 Primary Objective

To investigate the efficacy and safety of MT-7117 on time to onset and severity of prodromal symptoms associated with sunlight exposure in subjects with EPP.

2.1.2 Secondary Objectives

- To investigate the effect on sunlight exposure duration and tolerance in subjects with EPP.
- To investigate the effect on melanin density in subjects with EPP.
- To assess the effect of treatment on quality of life in subjects with EPP.
- To investigate PK in subjects with EPP.

2.1.3 Exploratory Objectives

- To evaluate skin biopsy samples from EPP subjects for exploratory biomarkers related to pathogenesis of EPP, inflammatory response, and the mode of action of MT-7117.
- To evaluate pharmacogenetics (PGx) including MC1R with single-nucleotide polymorphisms (SNPs), if applicable, as this could lead to pigmentation.
- To evaluate porphyrin and protoporphyrin levels.

2.2 Study Endpoints

2.2.1 Primary Efficacy Endpoint

- Change from baseline in average daily time (minutes) to first prodromal symptom associated with sunlight exposure between 1 hour post sunrise and 1 hour pre-sunset at Week 16 (Visit 8).

To calculate the average daily duration, a 14-day window on or before a visit/time-point (Week 2, 4, 6, 8, 10, 12, 14, and 16) will be used. For baseline, a 14-day window before Day one will be used. A 14-day window will be applied to similar situations for other efficacy endpoints.

2.2.2 Secondary Efficacy Endpoints

- Change from baseline in average daily duration (minutes) of sunlight exposure between 1 hour post sunrise and 1 hour pre-sunset without prodromal symptoms at Week 16.
- Change from baseline in average daily mean duration (minutes) of sunlight exposure between 1 hour post sunrise and 1 hour pre-sunset without prodromal symptoms. The daily mean duration is considered as multiple periods of sunlight exposure in each day and measurable by sum of duration of each period divided by number of periods.

- Total number of sunlight exposure episodes with prodromal symptoms during 16-week double-blind treatment period.
- The average daily mean intensity of the subject's prodromal symptoms during 16-week double-blind treatment period.
- Change from baseline in average daily duration (minutes) of prodromal symptoms during 16-week double-blind treatment period.
- The change from baseline and % change from baseline in melanin density at Week 8, 16, and 22 by skin segments. Average of 6 skin segments for the change from Baseline and % change from baseline in melanin density at Week 8, 16, and 22.
- Total number of pain events during 16-week double-blind treatment period.

2.2.3 Other Efficacy Endpoints

- Change from baseline for in-clinic sunlight exposure time (minutes) to the first prodromal symptoms.
- Total time (hours) during 16-week double-blind treatment period in duration of sunlight exposure between 1 hour post sunrise and 1 hour pre-sunset without prodromal symptoms.
- Total number of days subject is exposed to sunlight for any duration between 1 hour post sunrise and 1 hour pre-sunset without prodromal symptoms during 16-week double-blind treatment period.
- Change from baseline in average daily duration (minutes) of sunlight exposure between 1 hour post sunrise and 1 hour pre-sunset on Saturday without prodromal symptoms at Week 16.
- Change from baseline in average daily duration of sunlight exposure regardless of time of day without prodromal symptoms assessed at Week 16.
- The average daily mean intensity of the subject's pain events during 16-week double-blind treatment period.
- Change from baseline in average daily duration (minutes) of pain events during 16-week double-blind treatment period.
- Change from baseline for all total score and total score in each domain of physical function, anxiety, depression, fatigue, sleep disturbance, ability to participate in social roles and activities, pain interference, pain intensity in PROMIS 57.
- Patient Global Impression of Change (PGIC) and Patient Global Impression of Change_2 (PGIC_2).
- Quality of life and meaningful clinical benefit of MT-7117 using the exit interview questionnaire.

2.2.4 Safety Assessments

- Treatment-emergent adverse events (AEs) (including serious adverse events [SAEs] and adverse events of special interest [AESIs]).
- Physical examination.
- Vital signs (blood pressure, pulse rate, and body temperature).

Mitsubishi Tanabe Pharma Development America, Inc.

- Clinical laboratory examinations (hematology, coagulation, biochemistry, and urinalysis), including liver function markers (ALT, AST, GGT, ALP, direct and total bilirubin).
- 12-lead ECG at Baseline and EOT.
- Nevi appearance (assessed by a dermatologist or other qualified site staff). Any nevi undergoing change of clinical concern during active treatment will be biopsied for follow up.

2.2.5 Pharmacokinetic Assessments

Assessment of plasma PK: plasma concentrations of MT-7117 will be measured at protocol scheduled visits.

2.2.6 Exploratory Endpoints:

- Biomarker assessments using skin biopsy samples for those subjects who have given their consent.
- PGx analysis including MC1R, with SNPs for those subjects who have given their consent.
- Porphyrin and protoporphyrin levels.

3. STUDY DESIGN

3.1 Overall Study Design

This is a Phase II, randomized, double-blind, placebo-controlled study to assess the efficacy, tolerability, and safety of MT-7117 in subjects with EPP. The study consists of a 2-week screening period, a 16-week double-blind treatment period, and a 6-week follow-up period at Week 22. The total participation period is approximately 24 weeks.

This study is being conducted without regard to seasonality.

The study design is illustrated in Figure 3.1-1.

Subjects will attend Screening (Visit 1) up to 2 weeks before Randomization (Visit 2), in order to confirm eligibility and obtain pre-study safety assessments including nevi evaluation. Subjects will also be instructed how to use a sunlight exposure diary.

At Visit 2, subjects meeting eligibility criteria will be randomized in a 1:1:1 ratio to receive either [REDACTED], [REDACTED] of MT-7117, or matching placebo in a double-blind manner. Baseline average daily sunlight exposure time without prodromal symptoms (≤ 30 min and >30 min) will be used as stratum for the randomization. The first dose will be administered at Visit 2 following baseline assessment including in-clinic sunlight exposure test. Active or placebo [REDACTED] will be administered once daily in the morning with food.

Subjects will attend in-clinic visits at Weeks 4, 8, and 12 (Visits 5, 6, and 7, respectively) during which assessments will be performed. In addition, subjects will undergo mobile laboratory sample collection at Weeks 1 and 2 (Visits 3 and 4, respectively) to measure liver function markers (AST, ALT, GGT, ALP, direct and total bilirubin).

Subjects will attend the end of treatment visit at Week 16 or early termination (Visit 8). Following the last treatment visit, subjects will attend a follow-up visit at Week 22 or 6 weeks after early termination.

[figure not shown]

Figure 3.1-1 Study Design Schematic

3.2 Rationale for Study Design and Treatment Regimens

The objectives of this study are to obtain efficacy, tolerability, and safety data for the selected two doses (██████ and ██████ day) of MT-7117 and placebo when administered to subjects with EPP over a 16-week treatment period. A standard randomized, placebo controlled, double-blind treatment allocation is considered appropriate in order to obtain unbiased results in this study. Safety and PK/pharmacodynamic effects will be evaluated based upon these comparable data from the Phase I, MT-7117-E01 study.

Abnormal biochemical parameters related to the hepatic function were observed in rats and monkeys. In MT-7117-E01 human study, in subjects receiving 14 days of study drug, treatment emergent transaminase elevations were reported in 6/36 (17%) subjects receiving MT-7117 and 2/12 (17%) subjects receiving placebo. Of the six subjects receiving MT-7117 for 14 days reporting treatment emergent transaminase elevations, 4 had elevated baseline transaminase values. Therefore, frequent assessments of liver function markers are performed in this study.

The 16-week treatment period is considered a sufficient duration for evaluation of the efficacy and tolerability of MT-7117 for this study. Subjects will attend a follow-up visit 6 weeks after the end of treatment (or early termination) which is considered a sufficient duration to evaluate pigmentation recovery and safety of subjects. For the primary and secondary endpoints, the effect of MT-7117 on the duration of sunlight exposure will be measured using a sunlight exposure diary. Melanin density assessments are safe and routinely used in clinical studies of skin disorders and will be used in this study to assess the effect of MT-7117 on pigmentation. The effect of MT-7117 on quality of life will be assessed using questionnaires. The exit interview questionnaire will measure the clinical

Mitsubishi Tanabe Pharma Development America, Inc.

benefit of MT-7117 and perspectives of quality of life.

3.3 Risk:Benefit Statement

MT-7117 is an investigational drug, and its safety profile in humans has not yet been fully investigated. Therefore, all subjects will be closely monitored.

In embryo-fetal development study in mice, the total incidence of fetuses with skeletal anomalies was increased at [REDACTED], the lethal dose for adult female mice, with increased incidence of fused rib and fused sternbrae. Female subjects of child-bearing potential and male subjects with partners of child-bearing potential participating in the study will be required to use adequate contraception as defined in Section 4.7.1.

The Sponsor will undertake all reasonable measures, including thorough screening and safety monitoring procedures, to minimize the risk to subjects. Due to the potential of MT-7117 to increase liver function markers, liver function markers will be monitored at all planned study visits and assessment of AEs related to elevation of liver function markers and liver injury will be conducted. Additionally, subjects will be instructed to immediately stop study treatment if they meet any of the withdrawal criteria listed in Section 4.5.

3.4 Rationale for Dose Selection

The current study will investigate the efficacy and safety, of MT-7117 in subjects with EPP. In the MT-7117-E01 human healthy volunteer study, single doses up to [REDACTED] and multiple doses of up to [REDACTED] over 14 days in healthy male subjects, and single doses of [REDACTED] in healthy female subjects have been shown to be safe. Some reversible increases in skin pigmentation, consistent with the expected pharmacology, were noted following repeat dosing and appeared to show a dose-related trend. No SAEs occurred during Study MT-7117-E01. In summary, the proposed dose levels of [REDACTED] and [REDACTED] of MT-7117 once daily pose no appreciable safety concerns and are supported by previous human and animal experience.

4. SELECTION AND WITHDRAWAL OF SUBJECTS

The Sponsor does not operate a protocol waiver system for eligibility criteria.

4.1 Number of Subjects

A total of approximately 102 subjects are planned to be randomized in this study (34 subjects in each treatment group).

4.2 Recruitment Methods

A sufficient number of subjects will be screened to ensure the planned sample size will be achieved. Each subject will be screened according to the criteria described in Sections 4.3 and 4.4. Only subjects who are eligible for the study will be randomized.

4.3 Inclusion Criteria

A subject will be eligible for enrolment in the study if ALL of the following criteria apply:

1. Subjects provided written informed consent to participate.
2. Male and female subjects with a confirmed diagnosis of EPP based on medical history, aged 18 years to 75 years, inclusive, at Screening.
3. Subjects are willing and able to travel to the study sites for all scheduled visits.
4. In the Investigator's opinion, subject is able to understand the nature of the study and any risks involved in participation, and willing to cooperate and comply with the protocol restrictions and requirements (including travel).

4.4 Exclusion Criteria

A subject will NOT be eligible for this study if ANY of the following criteria apply:

1. History or presence of photodermatoses other than EPP.
2. Subjects who are unwilling or unable to go outside during daylight hours (e.g., between 1 hour post sunrise and 1 hour pre-sunset) during the study.
3. Presence of clinically significant hepatobiliary disease based on LFT values at Screening.
4. Subjects with AST, ALT, ALP $\geq 3.0 \times$ upper limit of normal (ULN) or total bilirubin $> 1.5 \times$ ULN at Screening.
5. Subjects with or having a history (in the last 2 years) of excessive alcohol intake in the opinion of the Investigator.
6. History or presence of melanoma and/or atypical nevus at Screening.
7. History of familial melanoma (defined as having 2 or more first-degree relatives, such as parents, sibling and/or child).
8. History or presence of pre-malignant skin lesion, squamous cell carcinoma, basal cell carcinoma, or other malignant skin lesions.

9. History or presence of psychiatric disease judged to be clinically significant by the Investigator and which may interfere with the study evaluation and/or safety of the subjects.
10. Presence of clinically significant acute or chronic renal disease based upon the subject's medical records including hemodialysis; and a serum creatinine level of greater than 1.2 mg/dL or a glomerular filtration rate (GFR) <60 ml/min.
11. Presence of any clinically significant disease or laboratory abnormality which, in the opinion of the Investigator, can interfere with the study objectives and/or safety of the subjects.
12. Pregnancy or lactation.
13. Females of child-bearing potential and male subjects with partners of child-bearing potential unwilling to use adequate contraception measures as described in the protocol.
14. Treatment with phototherapy within 3 months before Randomization (Visit 2).
15. Treatment with afamelanotide within 3 months before Randomization (Visit 2).
16. Treatment with cimetidine within 4 weeks before Randomization (Visit 2).
17. Treatment with antioxidant agents at doses which, in the opinion of the Investigator, may affect study endpoints (including but not limited to beta-carotene, cysteine, pyridoxine) within 4 weeks before Randomization (Visit 2).
18. Chronic treatment with prescription-based analgesic agents including but not limited to opioids and opioid derivatives such as morphine, hydrocodone, oxycodone or their combination with other analgesics or non-steroidal anti-inflammatory drug (NSAID, as Percocet and Vicodin-like prescription drugs) within 4 weeks before Randomization (Visit 2).
19. Treatment with any drugs or supplements which, in the opinion of the Investigator, can interfere with the objectives of the study or safety of the subjects.
20. Previous exposure to MT-7117.
21. Previous treatment with any investigational agent within 12 weeks before Screening OR 5 half-lives of the investigational product (whichever is longer).
22. [REDACTED]

- a. [REDACTED]
- b. [REDACTED]
- d. [REDACTED]

4.5 Withdrawal of Individual Subjects

A subject will be withdrawn from study if ANY of the following criteria are met:

1. The subject requests to voluntarily withdraw from further participation in study.
2. The subject is significantly noncompliant with the protocol.
3. Continuing in the study would be detrimental to the subject's safety in the opinion of the Investigator, e.g.,
 - a. The subject experiences intolerable AEs or SAEs.
 - b. The subject has clinically significant changes in safety parameters at any of the post-dose time points, as confirmed with a repeat assessment performed as soon as possible after the initial out-of-range result.
 - c. If there are any clinically significant adverse findings from post-baseline nevi evaluation, subjects will not be allowed to continue taking study medication (see Section 6.9.4). If biopsy findings are benign, subject may reinitiate study treatment based on investigators discretion.
 - d. Development of any clinically significant liver dysfunction, as follows:
 - i. ALT or AST $>6 \times$ ULN.
 - ii. ALT or AST $>4 \times$ ULN for more than 2 weeks.
 - a) Elevated total bilirubin $>2 \times$ ULN and ALT or AST $>2 \times$ ULN or
 - b) Symptoms consistent with liver dysfunction (e.g., fatigue, nausea, vomiting, abdominal pain or tenderness, fever, rash, eosinophilia $>5\%$) with concomitant ALT or AST values $>3 \times$ ULN.

Subjects (meeting above criteria) do not require withdrawal if alternative etiology is identified on discussion with the Study Medical Monitor.

Subjects meeting above criteria (with or without alternative etiology) should be reported as hepatic AE of special interest (AESI) (see Section 8.3).

These subjects will be discontinued from treatment but may be managed on study per the Investigator's discretion and followed per protocol (see Section 8.6). In addition, a subject may be withdrawn from treatment at any time for reason(s) other than those listed here.

If a subject is discontinued prematurely from the treatment or the study, the date the subject is withdrawn and the reason for withdrawal will be recorded on the site source documents and in the electronic Case Report Form (eCRF). Subjects who withdraw or are withdrawn from study treatment should be encouraged to complete all study visits and study procedures as outlined in the protocol.

In case of permanent discontinuation from study, the end of treatment and follow-up visit assessments should be performed, as completely as possible (Sections 5.3.2.7 and 5.3.3, respectively). Unresolved AEs and SAEs will be followed up on according to Section 8.10.

For discontinued subjects who will not revisit the clinic, the site will perform scheduled phone calls for the collection and source documentation for safety information (AEs, concomitant medication, and date of last dose of medication). Return of unused medication and any other materials (e.g., diary) will be performed by courier where allowed.

In the event that a subject elects not to return to the study site for the end of treatment or Follow-up visit, the Investigator must make every effort to contact the subject to review/capture all AEs, assess dosing compliance, review concomitant medication and make every effort to complete all end of study assessments.

Subjects withdrawn from the study following randomization onto double-blind treatment may not re-enter the study. Subjects withdrawn from treatment may remain on study and continue with study procedures off treatment based on the Investigators clinical discretion.

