6.9.5.2 Additional Laboratory Assessments

Additional laboratory safety evaluations will be performed at other times, if judged to be clinically appropriate, or if the ongoing review of the data suggests a more detailed assessment of laboratory safety evaluations is required. Any changes to the scheduled times of laboratory safety tests will be agreed with the Sponsor and documented in the Trial Master File.

The Investigator will perform a clinical assessment of all laboratory safety data. The Investigator will record the assessment as ‘normal’, ‘abnormal CS’, or ‘abnormal NCS’. Lab test abnormalities of clinical significance will be reported as AEs. Repeat lab tests or measurements will be performed if needed.

If subjects will meet treatment withdrawal criteria for elevated liver function tests, the subjects should be treated using standard of care as directed by the Investigator and followed until resolution (Section 4.5).

Table 6.9-1 Routine Laboratory Evaluations

Hematology:	
Hemoglobin	Mean corpuscular hemoglobin
Hematocrit	Mean corpuscular hemoglobin concentration
Platelet count	Mean corpuscular volume
Red blood cell count	White blood cell count and differential
Biochemistry:	
Alkaline phosphatase	Cholesterol
Aspartate aminotransferase	Triglycerides
Alanine aminotransferase	High density lipoprotein-cholesterol
Gamma-glutamyl transpeptidase	Low density lipoprotein-cholesterol
Potassium	Protein (total)
Sodium	Albumin
Chloride	Creatine kinase
Inorganic phosphate	Creatinine
Glucose	Ferritin

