8.3 Adverse Events of Special Interest

One AESI that will be considered during this study includes hepatic AESIs, defined as

- Clinically significant liver dysfunction, as follows:
 - ALT or AST >6 x ULN.
 - ALT or AST >4 x ULN for more than 2 weeks.
 - Elevated total bilirubin >2 x ULN and ALT or AST >2 x ULN, or
 - Symptoms consistent with liver dysfunction (e.g., fatigue, nausea, vomiting, abdominal pain or tenderness, fever, rash, eosinophilia >5%) with concomitant ALT or AST values >3 x ULN.
- Hepatic AEs or hepatic laboratory abnormalities that lead to study medication interruption or discontinuation (see Section 4.5).

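### Protocol 4.5(3d), as numbered, places the bilirubin and symptom liver criteria under the two-week transaminase item, while 8.3 lists all four at equal rank

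*Protocol*

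**What the plan says.** Section 4.5 item 3 covers withdrawal on safety grounds. Its sub-item d defines clinically significant liver dysfunction. Roman item i is ALT or AST above 6 x ULN. Roman item ii is "ALT or AST $>4 \times$ ULN for more than 2 weeks". The next line is labelled "a) Elevated total bilirubin $>2 \times$ ULN and ALT or AST $>2 \times$ ULN or", followed by b), symptoms of liver dysfunction "with concomitant ALT or AST values $>3 \times$ ULN". There is no iii or iv.

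The same section then directs: "Subjects meeting above criteria (with or without alternative etiology) should be reported as hepatic AE of special interest (AESI) (see Section 8.3". Section 8.3 defines the hepatic AESI with the same four criteria as bullets of one list, including "ALT or AST >4 x ULN for more than 2 weeks" and "Elevated total bilirubin >2 x ULN and ALT or AST >2 x ULN, or". A further 8.3 bullet covers hepatic events that lead to interruption or discontinuation, and refers back to 4.5.

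Section 3.3 says that "liver function markers will be monitored at all planned study visits" and that subjects will be told to stop treatment at once if they meet any 4.5 withdrawal criterion. Section 8.8 requires hepatic AESIs to be reported within 24 hours. SAP 7.12.1 counts subjects with an AESI and subjects with a TEAE leading to drug withdrawal.

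**The concern.** One set of liver criteria serves two purposes: withdrawal (4.5) and expedited reporting (8.3). Section 4.5 treats the sets as identical, since those who meet its criteria are to be reported under 8.3. The labels do not make them identical. If a) and b) are subordinate to ii, they apply only to a subject whose ALT or AST has already exceeded 4 x ULN for more than two weeks. If they stand alone, as in 8.3, they apply from above 2 x ULN (with bilirubin) or above 3 x ULN (with symptoms).

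At stake is whether an investigator who works from 4.5 as numbered recognises a bilirubin or symptom case as a liver withdrawal criterion. That recognition also triggers the 4.5 discussion with the medical monitor about an alternative cause. An investigator should not have to infer the structure of a liver rule.

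**Working it through.** No sample-size or power figure bears on this point. The check sets the two lists side by side and applies the labels.

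**1. Labels.**

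| Criterion | 4.5 label | 8.3 |
|---|---|---|
| ALT/AST >6 x ULN | i | bullet |
| ALT/AST >4 x ULN for more than 2 weeks | ii | bullet, same rank |
| Bilirubin >2 x ULN and ALT/AST >2 x ULN | a) | bullet, same rank |
| Symptoms with ALT/AST >3 x ULN | b) | bullet, same rank |

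In 4.5 each step down the hierarchy changes the label style: 3, then a to d, then i and ii, then a) and b). On that pattern a) and b) belong to ii. Four criteria of equal rank would have run i to iv.

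**2. Effective ALT/AST limit if a) and b) fall under ii.**
- a): max(4, 2) = 4 x ULN
- b): max(4, 3) = 4 x ULN

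Both stated limits are redundant under nesting.

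**3. Worked case: ALT 3 x ULN, bilirubin 2.5 x ULN.**

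| Criterion | 8.3 | 4.5(3d) as labelled |
|---|---|---|
| >6 x ULN | 3 > 6: no | no |
| >4 x ULN, more than 2 weeks | 3 > 4: no | no |
| Bilirubin | 2.5 > 2 and 3 > 2: **yes** | also needs ii: **no** |
| Symptoms | 3 > 3: no, whatever the symptoms | no |

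The subject is a hepatic AESI under 8.3 and meets no 3d criterion under 4.5 as numbered.

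**4. Who falls in the gap.** Anyone who meets the bilirubin or symptom bullet of 8.3, with ALT/AST not above 6 x ULN and not above 4 x ULN for more than two weeks. The documents give no rate for such subjects, so no count is offered.

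**5. Side note on the duration in ii.** Nominal liver draws from Week 4 to Week 16 fall on Days 29, 57, 85 and 113. The gaps are 57 − 29 = 85 − 57 = 113 − 85 = 28 days. Earlier draws fall on Days 8, 15 and 29, and 29 − 8 = 21 days. No section ties a repeat interval to item ii.

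**The case against.** The nested reading is weak as a statement of intent. Item ii ends with a full stop, and no connecting word makes a) or b) depend on it. Nesting would leave two stated limits with no function. The cross-reference to 8.3 shows the four criteria at equal rank. Indentation cannot be seen in the text reviewed, so the printed page may be clearer. Nor is 3d the only route to withdrawal: item 3 gives examples under the investigator's judgement, 3b covers confirmed clinically significant changes in safety parameters, and 4.5 allows withdrawal from treatment for unlisted reasons. All of this stands, and it makes a numbering slip the likeliest explanation. It does not remove the mismatch, which rests on the labels and not on the indentation.

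A reader might infer three stronger points that the documents do not support:

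- **That 4.5 and 8.3 would make sites stop different subjects.** Section 8.3 is a reporting definition, not a stopping rule, and it refers back to 4.5 for discontinuation.
- **That the draw schedule cannot establish more than two weeks.** Scheduled draws on Days 8 to 29 span 21 days, and consecutive four-weekly draws span 28. The criterion is also not confined to scheduled draws. Item 3b calls for a prompt confirmatory repeat, 5.3.5 provides unscheduled mobile liver draws, 8.6 requires follow-up of clinically significant results, and 6.9.5.2 adds "Repeat lab tests or measurements will be performed if needed". What remains is that no repeat interval is tied to item ii.
- **That Phase I transaminase elevations make the gap more pressing.** Section 3.2 gives 6/36 (17%) on MT-7117 and 2/12 (17%) on placebo, and 4 of the 6 had elevated baseline values. Those rates do not show a drug effect.

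**Conclusion.** The point holds as a structural inconsistency between 4.5(3d) and 8.3. As labelled, 4.5 subordinates two criteria that 8.3 treats as independent, and so makes their >2 x and >3 x ULN limits redundant. It is probably a numbering slip, but it sits in the operative liver withdrawal text and deserves correction for that reason.

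The extent is limited. Only subjects in the band in step 4 are affected, and item 3b and investigator judgement remain available for them. No efficacy analysis changes. The AESI count in the SAP rests on the 8.3 definition, which is clear in itself. The conclusion assumes that the labels in the text match the printed protocol. It takes no view on which structure or thresholds are clinically right.

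**What to change.** Reconcile 4.5(3d) and 8.3 so that both carry the same list with the same structure, and state in each whether every item stands alone. The sponsor decides which structure is intended. While editing, the sponsor may also wish to say how the duration in item ii is to be determined, since no repeat interval is tied to it, scheduled draws from Week 4 to Week 16 are nominally 28 days apart, and unscheduled draws are available under 5.3.5.

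The cost is a short protocol clarification (renumbering and one matching sentence in each section) and a notice to sites. The reconciliation itself needs no new assessment, sample or analysis.
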